4.5 General Information About Coronavirus

Coronaviruses are single-chain, positive-polar, enveloped RNA viruses. Because they have positive polarity, they do not contain RNA-dependent RNA polymerase enzymes, but in their genomes they encode this enzyme. They have rodlike extensions on their surfaces. These viruses are named as Coronavirus (Figures 1 and 2) based on the meaning of "corona", that is "crown" in Latin (Figures 1 and 2).

and Therapeutics Based on the Receptor-Binding Domain. Viruses. 2019 Jan 14;11(1)).

Figure 1 . Schematic Structure Of Covid-19 (Zhou Y, Yang Y, Huang J, Jiang S, Du L. Advances in MERS-CoV Vaccines and Therapeutics Based on the Receptor-Binding Domain. Viruses. 2019 Jan 14;11(1)).

[figure not shown]
[figure not shown]

Figure 2: New Coronavirus (betacoronavirus) electron microscope image (https://www.gisaid.org/,son access date: 20.01.2020)

Coronaviruses are in the Coronaviridae family, the Orthocoronavirinae subfamily. The Orthocoronovirinaea subfamily is classified into four genera and a number of subgenus under these genera: Alpha, Beta, Gamma and Deltacoronavirus genera. Viruses under these breeds can be found in humans, bats, pigs, cats, dogs, rodents and poultry (in domestic and wild animals).

The disease spectrum caused by Coronavirus in humans can range from simple colds to severe acute respiratory syndrome (Severe Acute Respiratory Syndrome, SARS). It can cause clinical manifestations in humans and animals with various degrees of respiratory, enteric, hepatic, nephrotic and neurological involvements. With the combination of Sanger sequencing, Illumina sequencing and nanopore sequencing, the first complete genome of the new genus Coronaviruses (COVID-19) was identified and three different strains were identified in bronchoalveolar lavage fluid samples. This virus has the typical features of the Coronavirus family and is located in the Betacoronavirus 2b line. The genomes of these strains and Betacoronaviruses have been shown to be closely related to bat SARS-like Coronavirus isolate Bat-SL-CoVZC45 (Figure 3).

Şekil 3: Yeni Coronavirus'un filogenetik ilişkisi (Tan W, Zhao W, Ma X, et al. A Novel Coronavirus Genome Identified in a Cluster of Pneumonia Cases — Wuhan, China 2019–2020, Notes from the Field, China CDC Weekly)

The virus responsible for COVID-19 is located under the Sarbecovirus subspecies in the genus Betacoronavirus, which it contains in SARS-CoV and MERS-CoV. The new nomenclature of the virus has been accepted as SARS-CoV-2.)

4.6 Turkish Beam Therapy Study of Viral Source

The Mechanism of Viruses Corona (crowned) Viruses

The mechanism of damage caused by SARS-CoV in cells, tissues and organs is still not fully understood. SARS-CoV must protect itself from the immune system of host cells in order to effectively replicate and reproduce. The virus, by escaping from the natural immune cells of the living creature it infects, negatively affects the mRNA of the host cell through nsp1 proteins, and seizes the metabolism of the host cell by modulating the host's ubicutination pathway with nsp3 proteins. After viral replication occurs in the host cell, cell damage is caused by viral-induced cytolysis or immunopathology. In studies, intestinal biopsy specimens of SARS patients have been detected by electron microscopy, viral factors as well as minor cytopathic effects or inflammations [11].

In transcriptome profiles of infected Caco-2 epithelial cells, a marked increase in strong immunosuppressive cytokine transformation growth factor β and antiapoptotic host cellular response

was observed. Again, in samples from infected animals (non-inflammatory secretions, diarrhea and feces), a large amount of viral factors were detected. The clinical or histopathological findings in the organs or tissues of the host cell are not only dependent on the presence of the relevant receptor and nucleus receptors or viral efficiency reflected by the viral load, but also in the determination of the inflammatory and apoptotic responses of the cell triggered by the virus, the regeneration power or functional reserve of the infected organ, the findings and the outcome of the infection. reported to be important [11].

In a study, it was stated that nsp1 expression in human lung epithelial A549 cells can increase the expression of chemokines (IP10, CCL3 and CCL5) in the NF- κ B pathway. IP10 of chemokines expressed on pneumocytes; it has been observed to be a potent chemoattractant for active cytotoxic T lymphocytes, natural killer cells, and monocytes, causing infiltrations in the lungs of SARS patients and interstitium and alveoli [12].

SARS-CoV dominates the lungs with simultaneous activation of proinflammatory chemokines and cytokines in the case of suppressing the IFN- β / α in type 2 pneumocytes without activating the natural immune response and IFN-induced genes and thus performing an uncontrolled viral replication in the cells. It has been reported to be in the position and be fatal [11].

In another study, it was found that the early induction of IP-10 and IL-2, as well as the overproduction of IL-6 and the lack of IL-10 production contributed to the immuno-pathological processes due to lung damage in SARS [13]. For these reasons, it is a known fact in many studies that chemokines produced by infected organs cause adaptive immune disorders and immune cell infiltrations in the lungs [14].

Source, Ways of Infection, Symptoms and Diagnosis

Source

It has not been clarified yet.

The origin of SARS-CoV-2 is still under investigation. Available data indicate wild animals illegally sold in the Huanan Seafood Wholesale Market.

Infection

The disease is transmitted mainly through droplets. In addition, it is transmitted to the droplets produced by sick individuals by coughing and sneezing, after they come into contact with the hands of other people, bringing their hands to the mouth, nose or eye mucosa and touching them.

The virus can be detected in the respiratory secretions of asymptomatic individuals, but the main infection is from the sick individuals. When the epidemiological characteristics of the cases in China were examined, it was observed that in some cases where the average incubation period was 5-6 days (2-14 days), it could extend up to 14 days.

The infectious time of COVID-19 is not exactly known. It is thought that it starts 1-2 days before the symptomatic period and ends with the disappearance of the symptoms.

Coronaviruses are generally viruses that are not very resistant to the external environment. There is a residence time that varies according to the humidity and temperature of the environment, the amount of organic substance it is expelled, and the texture of the surface it contaminates. It is generally accepted that it loses its activity within a few hours on inanimate surfaces. When interpreting the activity time on inanimate surfaces, it should be kept in mind that not only the activity of the virus continues, but also the duration of the contact.

Today, the contamination time and the duration of the external environment of COVID-19 are not known clearly. (Covid-19 guide T.R.Ministry of Health, March 23, 2020)

The first symptom of the disease is usually (> 38 C) high fever (15,19). In addition, feeling of restlessness, chills, sore throat, cough, muscle pain, pneumonia, diarrhea (10-20%), shortening of breathing depth or difficult breathing are among the most observed symptoms [16,19].

While radiological findings are normal in the early stages of the disease, consolidated areas due to focal interstitial infiltrates are detected in lung x-rays taken later on [16]. Leukopenia is observed in patients, while the decrease in lymphocyte numbers is noteworthy, lactate dehydrogenase, creatine phosphokinase and transaminase levels may increase. In addition to these findings in the future, most patients develop thrombocytopenia, that is, the number of blood platelets may decrease.

The disease may be subclinical in some people, as well as in severe and lethal form in people with weakened immunity (children and elderly people) or diabetic people. People with complications such as hepatitis are also at higher risk for serious complications [11, 17, 19].

For the diagnosis of SARS-COV, blood samples, nasal / throat cultures, stool and sometimes urine or tissue samples tests from patients should be studied in laboratories with biosafety level 3 (BSL-3) (11,19). PCR tests performed with reverse transcriptases (RT-PCR) specifically targeting the corona viruses specific ORF 1b or nucleoprotein gene, antigen tests with monoclonal antibodies or monospecific polyclonal antibody against N protein and various serological and immunofluorescent tests performed in fluorescent dyes in the laboratory. These are the basic tests used for diagnosis [11]. The immunological tests used for diagnostic purposes are less sensitive than RT-PCR, but they are known as very sensitive and specific tests in both methods [11]. Immunofluorescent antibody (IFA) tests. its biggest disadvantage is that it can give false results in the initial stage of the disease. However, these tests are still used as screening tests that are very effective and fast, especially after the 5th day of infection (11; 16).

Infection Control and Isolation

Isolation measures should be continued during the period in which the patient is in the health facility, since the virus excretion time and infectious time are not known today.

COVID-19 is thought to be of zoonotic origin, and human-to-human transmission is shown in the latest data. For this reason, standard, droplet and contact isolation measures should be taken in cases where the presence of COVID-19 is considered.

Hospitalization:

• Possible cases are followed up in 2nd and 3rd level hospitals.

• The finalized cases are followed in the 2nd and 3rd stage hospitals or in the hospitals designated in the province.

• Patients who need intensive care from the cases that are finalized are followed up in isolation rooms in the 2nd and 3rd level intensive care units.

Standard infection prevention and control measures should be applied in healthcare facilities. In addition, the application of contact and droplet protection measures should be continued until the patient becomes asymptomatic.

The following infection prevention and control measures should be applied to prevent the spread / transmission of the disease at the health facility.

As the personal protective material required for personnel who will come closer to 1 meter closer to certain / possible COVID-19 cases;

1. Gloves,

- 2. Gowns (non-sterile, preferably liquid impermeable and long sleeves),
- 3. Medical mask (surgical mask),

4. At least N95 / FFP2 mask (Only during the process causing droplet / aerosolization) *,

- 5. Face Guard,
- 6. Glasses **,
- 7. Liquid soap,
- 8. Alcohol based antiseptic,

Sufficient amount should be kept available by inpatient health institutions.

It can be used by making decisions on the basis of overalls, bones and foot protectors, especially in cases where intensive contact with the patient's body fluids and secretions can occur.

Recommendations for the use of Personal Protective Equipment

https://hsgm.saglik.gov.tr/depo/covid19/rehberler/covid_table_hsgm.pdf?type=fil to

* Process that causes droplet / areosolization; aspiration, bronchoscopy and bronchoscopic procedures, intubation, respiratory tract sampling

** Reusable glasses are cleaned according to the manufacturer's recommendation. If there is no special recommendation, it should be disinfected with 70% ethyl alcohol and left to dry on its own in an appropriate environment. In case of using the glasses again, the health institution is instructed where the glasses will be removed, stored and disinfected.

Treatment Methods

In the treatment of SARS-CoV, corticosteroids, which affect the whole body, which is known as the immune modulator treatment method, and have anti-inflammatory and immunosuppressive effects, ensure early recovery of the fever and more harmless radiographic leaks. Ribavirin, which is the nucleoside analogue used in treatment, is known as an agent that has antiviral activity against many DNA and RNA viruses. Ribavirin blocks the viral replicase polyprotein and stops RNA replication. Another method used in the treatment of SARS-CoV is the protease inhibitor (18,19).

Lopinavir-ritonavir common formulation, which is also used in the treatment of HIV infection, can be used in conjunction with ribavirin in the early stages of the disease, and may help antiviral therapy (18,19). However, additional research is needed to develop new treatment methods such as additional antiviral treatments, RNA silencing methods, anti-monoclonal antibody, anti-viral peptides and vaccines, as well as the use of interferon and general steroids in the treatment of immune-mediated lung injuries (16,19).

COVID-19 Outpatient Clinic or Emergency Admission and Follow-up (for cases aged 16 and over) Patients from the triage-orientation area are evaluated in terms of COVID-19 case definition, with the mask attached.

-COVID-19 fits into the definition of the case, are taken to the specified area.

- Appropriate personal protective equipment (gown, medical mask, goggles / face protector, gloves) are entered in the area where the patient is located.

- The patient's anamnesis is taken,

- Inspection is done

Vital findings are checked (heart rate, rhythm, respiratory rate, blood pressure, body temperature and oxygen saturation are checked if conditions are appropriate)

- The patient's general condition is unstable; respiratory and circulatory support is provided and hospitalized to the relevant service *,

- The patient, whose condition is stable, is examined

- Inspections are requested; - Blood tests:

Complete blood count, Urea, creatinine, sodium, potassium, chlorine, AST, ALT, total bilirubin, LDH, CPK, D-dimer, troponin, C-reactive protein values may be requested when the doctor deems it appropriate.

- Imaging: A chest X-ray is taken and evaluated, and Lung CT is taken with the appropriate technique in the following described situations.

- Clinical decision should be made according to the history and examination findings in pregnant patients who cannot have CT.

Lung BT:

1- Fever + cough - Chest X-ray natural: Low-contrast CT without contrast

2- Fever + cough - Chest X-ray diagnostic / not diagnostic: Low-dose CT without contrast

3- Fever + cough + comorbid disease or advanced age (60 years old and above) + non-diagnostic chest radiography: Full-dose CT without contrast, contrast CT is taken if there is indication for another disease

1- Uncomplicated disease table

a. No underlying disease (cardiovascular diseases, DM, HT, cancer, chronic lung diseases, other immunosuppressive conditions)

b. Having symptoms such as fever, muscle / joint pain, cough, sore throat, nasal congestion

c. Patients with normal pulmonary film and / or pulmonary tomography

A respiratory sample is taken for testing using personal protective equipment for COVID-19.

It is sent to the isolation areas or home designated by the Provincial / District Health Directorate to monitor symptoms with isolation suggestions outside the hospital, and their daily follow-up is done by phone.

If the test is positive, the patient is hospitalized and oseltamivir and hydroxychloroquine are started. If it turns out negative; If the disease is resolved, act according to alternative diagnosis. Patients who have a negative test but worsen symptoms are called to the hospital for re-evaluation. To rule out COVID-19, a second respiratory tract sample is taken and the test is requested. It continues to be followed up, inpatient or inpatient, depending on the clinical condition of the patient.

2-Pneumonia / Those that fit the definition of severe pneumonia I.

a. Respiratory rate <30 / minute, SpO2 level above 90% in room air and

b. Patient with signs of pneumonia on chest radiograph or tomography

It is deposited in the relevant service. A respiratory sample is taken for COVID-19. The test is done. Without waiting for the test result, oseltamivir and hydroxychloroquine are started in accordance with the treatment algorithm. The test result is followed. II

a. It has a follow-up (\geq 30 / minute) with SpO2 level below 90% in the room air,

b. Patient with signs of pneumonia or developing acute organ dysfunction on chest X-ray or tomography

deposited in the intensive care unit. A respiratory sample is taken for COVID-19 and the test is performed. Without waiting for the test result, oseltamivir and hydroxychloroquine are started in accordance with the treatment algorithm. The test result is followed.

If the test results are positive; the result is notified to the Provincial Health Directorate and acts according to the case management scheme.

If the test results are negative;

If there is worsening of clinical findings in outpatients, the test is repeated.

If no alternative diagnosis can be made in patients who are hospitalized, the test is repeated. * If there are the following intensive care indications in the hospitalization process, the

patient is admitted to the intensive care unit and to the relevant service in other conditions. . Intensive Care Unit Hospitalization Indications:

- Respiratory rate ≥ 30

- Dyspnea and breathing difficulties findings

- Cases with oxygen saturation below 90% despite nasal oxygen support of 5 liters / minute and above

- Cases with partial oxygen pressure below 70 mmHg despite nasal oxygen support of 5 liters / minute and above

- PaO2 / FiO2 <300

Lactate> 4 mmol / L

Bilateral infiltrations or multi-lobar involvement on chest x-ray or tomography

- Hypotension (systolic blood pressure <90 mmHg,> 40 mmHg drop from usual SKB, mean arterial pressure <65 mmHg)

- Skin perfusion disorder

Organ dysfunction such as kidney function tests, liver function test disorder, thrombocytopenia, confusion

Presence of immunosuppressive disease

- The presence of more than one disease at the same time

- Troponin height, arrhythmia

(Covid-19 guide T.R.Ministry of Health, March 23, 2020)

Given all these issues,

The treatment method we developed with the UVC method, especially affects the nucleic acids in the DNA and RNA chains of bacteria, fungi and viruses, disrupts the connective structure and inactivates the pathogens that cause infection. The Ultraviolet-C (UVC) beam used is an alternative to alternative methods to existing methods used in the treatment of localized infections. The inactivation mechanism of UVC is accomplished by providing dimerization of microorganisms to the genetic material in the nucleus or pyrimidine molecules in the nucleic acids in the virus. Thus, the proliferation of nucleic acids (microorganisms) is inhibited and inactivated. The UV-C spectrum, especially the range of 250-270 nm, is strongly absorbed by the nucleic acids of a microorganism and at the end of this process it performs its breakdown.

4.7 Selective Permeable Effective Ultraviolet Wavelength Determination to be Applied

The ultraviolet C (UVC) beam is an alternative methods to existing methods used in the treatment of localized infections. Some drug resistant microorganisms have also been found to be sensitive to UVC irradiation. UV radiation can kill all kinds of microorganisms with its short wavelength and high energy. The greatest antimicrobial activity is in the wavelength region of 250-264 nm.

Contrary to what is known, UVC, selected with appropriate doses, can selectively inactivate microorganisms while maintaining the viability of mammalian cells and has also been proven to promote wound healing. UVC (200nm - 280 nm) has been proven to cause less damage to tissue than UVB in animal studies. [one]. Although UVC can cause DNA damage in mammalian cells, it can be quickly repaired by DNA repair enzymes. [one]. In summary, UVC is an innovative treatment method of our age as an alternative approach to existing methods used for localized infections, single stranded RNA and double stranded DNA viruses, especially for the treatments caused by highly antibiotic-resistant microorganisms. UVC should be used in such a way that side effects are minimized and the resistance of microorganisms to UVC is prevented.

4.8 Benefits / Risks:

Risks from implementation:

-Vascular rupture

- -If the guide cannula moves out of the target, tissue damage and radiation-related damage
- -Depending on the place of application, thrombosis

-Pulmonary tissue damage

- -Pnomotoraks
- -Hemotoraks

Risks from the beam device: Retinal damage and vision loss

The risks mentioned above are due to the fact that the work team is selected from experienced and competent people.

has been minimized. They will also undergo a separate training for applications. Already intensive care and intubation in intratracheal / pulmonary / intravascular interventions In addition to the risks that may occur under the

It stands out.

On the other hand, it is compulsory to use ultraviolet-proof glasses as specified in the protocol for the patient who performs the application. There is no additional risk that may arise from the device.

However, the benefit that will arise from beam application is very high compared to these risks.

With the treatment we envisaged, survival will increase significantly.

We think that the duration will be shortened and superinfections will be prevented. Summarized benefit / risk

we estimate that the rate is very high and the risk is minimal

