5.4 Applied Treatment

5.4.1. Treatment Definition and Method

The system should be inserted into the Invamed Steerable Catheter (disposable CAMERA CATHETER) via an ultraviolet / laser light source and the fiberoptic cables connected on it. Ultraviolet / laser light from the end of the fiberoptic system destroys microorganisms (including viruses) at the end of a second-long application. The system is based on the basis of the elimination of microorganisms in these areas with a low dose of UV light / laser application from the catheter by sending it directly to the body cavities via a fresroptic catheter, intrarespiratory, intravascular (used with intracat). With the help of Invamed Steerable Catheter (Disposable Camera Catheter), UVC beam applied with a catheter inserted into the lungs and accompanying fiberoptic are interventions related to the reduction or elimination of infection. With the application of ultraviolet light / laser beam, the patient is treated with a significant reduction / destruction of the microorganism and inflammation burden in the patient's body. The proposed treatment is an antimicrobial treatment strategy, and it is recommended to combine supportive treatments with this process in terms of a holistic treatment strategy based on the clinical course of the disease. UVC and Laser application will be performed on the research arm, together with intravascular and intrarespiratory application.

Effective Dose: The blood / tissue infected with microorganism, the effective dose required to destroy the microorganism population: 2 mj / cm2 [4]

5.4.1.1. Intravascular UVC Application Process Steps:

- Hands are washed in accordance with the "Hand Hygiene and Glove Directions for Use".
- The patient is given a position in which he / she can feel comfortable according to the application area.
- A protective cover is placed under the interference area.
- Sterile Gloves are worn. IV cannula outer cover is opened.
- Fiberoptic catheter system is slowly pushed into the IV cannula.
- Approximately 5 cm cut from the tip of the catheter is adjusted to remain in the intrvascular area and UVC application is started.
- The Fiberoptic catheter is with drawn slowly after UVC administration at the specified time and strength.
- In order to apply the energy required for microorganism inactivation with the power value applied with UVC source, 200 mj / cm2 energy should be applied for 30 minutes +/- 5 minutes.

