- The patient is given 100% oxygen for 2 minutes,
- Sterile gloves are worn,
- Steerable catheter is advanced through the airway to the orotracheal region in accordance with the aseptic technique.
- Fiberoptic UVC is advanced through the line catheter in accordance with the aseptic technique.
- When the catheter inserted through the nose or mouth reaches the pharynx, the patient is coughed and the catheter is advanced in the inspiratory phase and UVC is applied.
- The patient is monitored throughout the procedure,
- After the procedure, the patient is given 100% oxygen for 1 minute.
- The time required for the tracheal application of the energy required for the microorganism inactivation with the power value applied by the UVC source, these values are indicated in the table below according to the trachea diameter. (Table 1).

Respiratory Application Diameter Mm	Power Per Unit Area	Application time	Energy Required
Diameter (mm)	mw/cm ²	S	mj/cm ²
5	67,90	2,95	200
10	61,11	3,27	200
15	57,72	3,47	200
20	55,00	3,64	200
25	52,28	3,83	200
30	49,57	4,03	200
35	46,85	4,27	200
40	44,14	4,53	200
45	42,10	4,75	200
50	40,74	4,91	200
	(Table	1)	

Depending on the trachea diameter in the drawn CT, force should be applied for the time specified in the relevant table. The amount of energy to be transferred to the tissue is arranged according to the table with each advance of the fiberoptic catheter 1 cm.

The healthcare personnel who receive the treatment, taking into consideration the clinical condition of the patient, should not exceed the maximum application time (30 min \pm 5 min in intravascular applications, 5 min \pm 1 min in intrarespiratory applications), and this should be at most 5 days. should apply in accordance with the protocol.

CLINICAL WORK TREATMENT AND FOLLOW-UP PROGRAM								
Evaluation	Screening Visit (Day 0)	Inclusion / Randomization (Day 0)	Treatment Visit (Day 1)	Treatment Visit (Day 2)	Treatment Visit (Day 3)	Treatment Visit (Day 4)	Treatment Visit - Final (Day 5)	Label Period / Follow-up Visit (Day 7&15)
Informed Volunteer Consent Form	Х							
Demographic information	X							
Medical history / General physical examination	X	X	X	X	X	X	X	x
Current treatments (drugs)	X	X	x	x	X	X	X	
Biochemistry, Complete blood count	X	X	x	x	X	X	X	x
Radiological Imaging	X	X		X			X	X
Vital findings	X	X	X	X	X	X	X	X
Include / exclude criteria		X	X	X	Х	X	X	
Pregnancy test (serum / urine)	X	X						
randomization		X						
Dose diary			X	X	X	X	X	

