Like all other pathogen inactivation methods, the advantage of the UVC technique is undoubtedly the absence of photosensitive compound, and therefore even the receiver of inactivated PCs is not exposed to a chemical compound trace. Clinically relevant G(+)and G(-) bacteria and small non-enveloped viruses are effectively inactivated. In addition, it minimizes the risk of transmission of protozoa such as Tripanosoma cruzi and Leishmania infantum and effectively inactivates Babesia divergens. The UVC method is effective for leukocyte inactivation, including T cells responsible for TA-Gvhd. Therefore, when patients at risk of developing TA-GvHD need PC transfusions, UVC irradiation is sufficient and no additional irradiation (with radiators) is required. In addition, pilot studies show that UVC irradiation not only inhibits cytokine synthesis, but also protects receptors against antigen alloimmunization. However, there are limitations such as low activity against HIV (only 1 day reduction) and increased secretion of platelet chemokines. [10].

2. Inactivating hepatitis C virus in donor lungs using light therapies during normothermic ex vivo lung perfusion

A significant number of organ donors are in the risk group for hepatitis C virus (HCV) infection. Here, studies have been carried out to evaluate the reliability and effectiveness of UVC rays in lung transplantation, where the risk of HCV transmission of UVC beam applied to the lungs before transplantation has been minimized significantly. [3].

The presence of organs is a limiting factor for lung transplantation and leads to significant mortality rates on the waiting list. The use of organs from donors with infectious viral infections such as hepatitis C virus (HCV) will increase organ donation, but these organs are generally not recommended for transplantation due to the high risk of contamination. Here, a method for the treatment of HCV infected human donor lungs that prevents transmission of HCV has been studied. In combination with germicidal light-based treatments, physical viral clearance

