Using UVC light sources, such as antiseptic lamps for disinfection of blood products, therapeutic treatment of whole blood and the treatment of human body or implant-related infections: Mohr and others have developed a method of pathogen inactivation for blood products using UVC irradiation. Under constant shaking with blood, he exposed it to UV light in a UV-permeable bag. They concluded that an exposure dose of 500 J / m2 resulted in an acceptable disinfection rate in their solution without sacrificing the quality of platelets. At 1500 J / m2, in vitro UVC (254 nm) irradiation of the platelet suspension layer caused a decrease in the number of platelets. UVC irradiation in biological systems has a large number of effects. The inactivation of UVC viruses and bacteria is also based on this mechanism [7].

6. Ultroviolet C lradiation for Prevention of Centrol Venous Catheter-related Infections: An in Vitro Study

With the long-term use of central venous catheters in the body or vein, a biofilm layer is seen in which microorganism development occurs between the catheter surface and the vessel wall. The

application of 254nm UVC beam applied with the help of a fiberoptic in the catheter lumen with the help of a power source has proven to significantly decrease the microorganism population (grampositive bacteria, gramnegative bacteria, fungi) present on this surface. When applying to the central venous catheter inner lumen for 60 seconds with an energy of 3.6 Joule during application, 99% microorganism inactivation was achieved. [8].

7. Ultraviolet-C Light for Treatment of Candida albicans Burn Infection in Mice

In this study, the use of 254nm UVC light was investigated for the treatment of Candida Albicans infection in third degree burns in mice. As a result of testing UVC on mouse skin, no serious damage was observed in the skin tissue and it was concluded that there was an increase in the loss of fungal lumenscence. It was concluded that UVC light therapy was effective on mice with this infection. [5]. Candida albicans is the most common fungal pathogen responsible for fungal infection in burn patients, and is the fourth most common organism found in blood cultures in intensive care unit patients.

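### Section 4.8 rules out further device risk without addressing the protocol's own in vitro platelet finding, and no by-arm platelet comparison is named

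*Combined protocol and SAP*

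**What the plan says.** Section 4.8 lists risks of the procedure: vascular rupture, tissue and radiation-related damage if the cannula strays, thrombosis, pulmonary damage, pneumothorax and hemothorax. It then gives one line for the device, "Risks from the beam device: Retinal damage and vision loss", makes protective glasses compulsory, and closes with "There is no additional risk that may arise from the device".

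The reference studies printed after Section 6 contain two statements on platelets. Item 5 reports that "an exposure dose of 500 J / m2 resulted in an acceptable disinfection rate in their solution without sacrificing the quality of platelets", and that at 1500 J/m2 in vitro "irradiation of the platelet suspension layer caused a decrease in the number of platelets". The closing text of item 1 names "increased secretion of platelet chemokines" among the limitations of the UVC method. That is an effect on platelets, but not a count.

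For the intravascular route, Section 5.4.1.1 says "200 mj / cm2 energy should be applied for 30 minutes +/- 5 minutes". The text before the visit schedule limits treatment: "and this should be at most 5 days". In the schedule, the row "Biochemistry, Complete blood count" is marked at both Day 0 columns, on Days 1 to 5, and at the Day 7 and 15 follow-up.

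Section 5.6 lists 19 adverse effects, among them bleeding, hematoma and embolization, but not platelet count or thrombocytopenia. Section 6 promises that safety will be examined at the interim report. The tests it names concern intensive care stay, survival and the contribution to treating infection. Descriptive statistics are named for demographic data only.

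**The concern.** A risk section should deal with adverse signals in the plan's own references, if only to explain why they do not apply. Section 4.8 neither mentions the platelet finding nor argues against it, and it concludes that risk is minimal.

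The analysis gap matters because of the population. Section 5.2 gives thrombocytopenia as an example of organ dysfunction at entry, Section 4.6 describes it as part of the disease, and Section 5.3 does not exclude low platelets. If a treated patient's count falls, the person reviewing that case has a ready explanation in COVID-19. Bleeding and hematoma show only the clinical consequences of a fall. The randomised comparison is the strongest way to separate device from disease, and the plan does not say that it will be made.

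**Working it through.** **1. Doses in one unit.** 1 mJ/cm2 = 10 J/m2.

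| Source in the protocol | As stated | mJ/cm2 | Platelet result given |
|---|---|---|---|
| Item 5, lower dose | 500 J/m2 | 50 | quality preserved |
| Item 5, higher dose | 1500 J/m2 | 150 | number reduced, size not given |
| Item 1, platelet bags | 0.4 J/cm2 | 400 | no platelet count given |
| Section 5.4.1.1, intravascular plan | 200 mJ/cm2 | 200 | none |

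The nominal plan lies above the level at which the protocol reports a fall.

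**2. Are the doses comparable?** Spread evenly over 30 minutes, 200 mJ/cm2 is 200 / 1800 s = 0.11 mW/cm2. At that rate, reaching 150 mJ/cm2 takes 150 / 0.111 = 1350 s, or 22.5 minutes in the beam. With an assumed transit of 1 to 10 s, blood passing the tip receives 0.1 to 1.1 mJ/cm2 per pass. If the irradiance were instead near the airway values in Table 1 (40.74 to 67.90 mW/cm2), 150 mJ/cm2 would be reached in 150 / 67.90 = 2.2 s to 150 / 40.74 = 3.7 s. The protocol does not settle which applies, so the table shows a signal to address and does not give patient exposure.

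**3. What a by-arm comparison could show.** The plan gives no figure to reproduce. Section 1.0 gives 25 per arm; Section 6 gives an interim look at 100 per arm. For a baseline-adjusted mean difference, the 95% CI half-width in SD units is t(0.975, 2n−3) × √(2/n) × √(1−r²). The baseline correlation r is assumed.

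- n = 25, r = 0.5: 2.012 × 0.283 × 0.866 = 0.49
- n = 25, r = 0.7: 2.012 × 0.283 × 0.714 = 0.41
- n = 100, r = 0.5: 1.972 × 0.141 × 0.866 = 0.24
- n = 100, r = 0.7: 1.972 × 0.141 × 0.714 = 0.20

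If the SD of the lowest count is 60 to 100 ×10^9/L (assumed), the half-width at 25 per arm is about 24 to 49 ×10^9/L. The difference detectable with 80% power at a two-sided 5% level is 0.58 to 0.70 SD, about 35 to 70 ×10^9/L.

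**4. Effect of early deaths.** A patient who dies early has fewer counts, which tends to raise the lowest one seen. This was simulated with no device effect, counts on Days 1 to 5, correlations of 0.5 to 0.85 between days, and deaths of 10% in the UVC arm against 20% to 30% in controls (all assumed). With no fall before death, the adjusted difference shifted by 0.02 to 0.09 SD, making UVC look worse. With counts falling by 0.25 to 0.5 SD per day in patients who die (assumed), the shift reversed to 0.01 to 0.15 SD, which would mask a device effect. The direction therefore depends on what happens before death. At 100 per arm, 0.15 SD is not small against a half-width of 0.20 to 0.24 SD.

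**The case against.** The sentence in Section 4.8 follows a list of risks and the rule on glasses, in a stretch of broken translation. It reads most naturally as nothing beyond the above. A reader might infer that the protocol denies all device risk; the text does not support that, since retinal and radiation damage are listed. What stands is that no blood-cell effect is among the listed risks.

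The dose evidence is thin. Item 5 describes an irradiated platelet suspension, gives no size for the fall, and summarises a source whose title concerns estimating the dose received by blood outside a catheter tip, so that source may hold the missing figure. Item 5 also credits its 500 J/m2 to what appears to be the group whose platelet study is summarised in item 1 at 0.4 J/cm2, eight times as much (4000 / 500). This limits the claim to an unaddressed signal. It does not justify saying that no further device risk may arise.

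Safety monitoring exists: blood counts at every visit, adverse events from randomization, and bleeding and hematoma in Section 5.6. Daily within-patient change and the dose diary are also evidence, though weaker than a randomised comparison. A reader might infer that platelets go unmonitored; the schedule shows otherwise. The gap is in the named outcome and analysis. It is also fair that the wider gap is the lack of any laboratory safety comparison. Platelets are chosen because the protocol's own summary points to them.

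**Conclusion.** The concern holds in a limited form. Section 4.8 draws a risk conclusion that leaves out a platelet finding in the protocol's own source summaries, and no platelet or other laboratory comparison by arm is named. The documents do not show that the treatment lowers platelets. A reader might infer from 200 against 150 mJ/cm2 that patients would be exposed above a harmful level; this is not supported, because the dose per platelet in flowing blood is not stated and the protocol leaves the irradiance at the fiber tip open.

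At 25 per arm the comparison would be informative only for a large fall, with a half-width of about 0.41 to 0.49 SD. That rests on assumed correlations of 0.7 to 0.5; the SDs in count units and the death rates are also assumptions. It is a cheap improvement of minor to moderate severity.

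**What to change.** 1. **Section 4.8.** Replace the sentence on no additional device risk with a statement that a possible effect on platelets is not excluded. Cite the item 5 findings at 50 and 150 mJ/cm2 with their limits: in vitro, and dose per platelet not stated in this protocol. Note that item 1 describes platelet irradiation at 0.4 J/cm2 without a platelet-count result, so it neither supports nor excludes the effect.

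2. **Section 6.** Add one safety outcome: the lowest platelet count over Days 1-7, adjusted for the last Day 0 count before the first UVC session, with the same time point used in controls. Report the by-arm difference with a 95% CI and make no significance claim. Including Day 7 catches a fall after the last sessions.

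3. **Supporting table by arm.** Show counts on Days 1-5, 7 and 15, the number measured, deaths by day and platelet transfusions. State that unequal early deaths can bias the lowest count in either direction.

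4. **Termination rule.** Keep this outcome outside the two-event rule in Section 5.6, so that thrombocytopenia from the disease cannot stop the study.

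The cost is a few sentences, one table and possibly one record field for platelet transfusion. No extra blood is drawn. The downside is a wide interval at 25 per arm, and the report should say that such an interval is not evidence of no effect.
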